4.3.2 Randomization

Subjects will be randomized 1:1 to receive either combination treatment with IVIG plus SMT or SMT alone. A central randomization will be used for this study. A randomization list containing the randomization numbers and the corresponding randomized treatment assignments will be generated by using a SAS program and be stored in a secured area that is only accessible to the randomization team. Once a subject has met eligibility criteria, a site personnel will email a randomization request to the randomization center. A randomization center operator will randomize the subject by selecting the next available randomization slot in the randomization list, starting at the top of the list and moving toward the bottom of the list, and reply to the email with the randomization number and corresponding randomized treatment assignment included. The personnel will communicate the randomization number, date/time, and treatment assigned to the site study staff, so that the information can be entered in the case report form.

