## 3.2 Treatment

### 3.2.1 Randomization Scheme and Treatment Arm Assignment

Subjects will be randomized 1:1 to receive either combination treatment with Gamunex-C plus SMT or SMT alone. A central randomization will be used for this study. A randomization list containing the randomization numbers and the corresponding randomized treatment assignments will be generated and be stored in a secured area that is only accessible to the randomization team.

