## 4. GENERAL CONSIDERATIONS FOR DATA ANALYSIS

Unless otherwise specified, continuous variables will be summarized using descriptive statistics (n, mean, standard deviation, median, minimum, and maximum). Categorical variables will be summarized showing the number and percentage of subjects within each category.

Summary results will be provided for each treatment group. All tabulations will be based on pooled data across centers.

All statistical tests will be two-sided and tested at the 5% level of significance.

Analyses will be performed using SAS for Windows statistical software, version 9.4 or higher (SAS, Cary, NC), except where other software may be deemed more appropriate. In the event that other software is used to perform some analyses, the details will be provided in the Clinical Study Report.

■ will perform all efficacy and safety analyses described in this SAP.

Subject data will be listed, sorted by treatment group and subject number. When applicable, listings will be additionally sorted by visit and assessment date/time.

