### **Ordinal scales**

- a) The absolute value and change from baseline in the Ordinal scale from Day 1 through Day

29 will be summarized by treatment group and visit using descriptive statistics.

Mean change in Ordinal scales through Day 29 will be evaluated by fitting a linear mixed-effects model for repeated measures (MMRM). The model will include change from baseline in Ordinal scale as the repeated dependent variable; treatment (as a class variable), visit (as a class variable), and treatment-by-visit interaction as fixed effects; baseline Ordinal scale, age and gender as covariates; and measures within subject at each visit as a repeated measure. An unstructured covariance matrix will be used to model the within-subject error. If the fit of the unstructured covariance structure fails to converge, a compound symmetry covariance structure will be used. Parameters will be estimated using restricted maximum likelihood with the Kenward-Roger method for calculating the denominator degrees of freedom. Data collected starting at the Day 2 visit and up to the Day 29 visit will be included in this analysis. Missing data will not be imputed. From this model, the least-squares (LS) means and 95% CIs for each treatment group, the treatment difference in the LS means, the 95% CI for the difference, and the associated p-value will be reported on Days 15 and 29, as well as for the average across all post-baseline visits.

- b) The proportion of subjects in each severity category of the 7-point Ordinal scale at Day 15 and Day 29 will be tabulated. The difference in severity category distribution between treatment groups at Day 15 and Day 29 will be examined using proportional-odds cumulative logit model. The cumulative logits model will compare lower ordinal scales to higher ones, or equivalently, less favorable outcomes to more favorable ones. The model may be adjusted for baseline characteristics such as age and gender, if appropriate. The estimated odds ratio and 95% CI will be presented. Graphical illustrations of the fitted model will also be presented for Day 15 and Day 29.

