### **9. SAMPLE SIZE AND POWER CALCULATIONS**

Because of the urgency and lack of previous prospective COVID-19 data, sample size estimation remains incompletely defined; however the size of this pilot study is commensurate with other Phase 2 investigations ongoing during the COVID-19 pandemic. Approximately 100 subjects are allowed to be randomized as part of a humanitarian effort against COVID-19.

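### The Day 15/29 proportional-odds model prespecifies neither the baseline ordinal category nor any other covariate

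*SAP*

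**What the plan says.** Part (b) of Ordinal scales in SAP 6.2 says that the difference in category distribution between arms at Day 15 and Day 29 "will be examined using proportional-odds cumulative logit model". Its only sentence on covariates is "The model may be adjusted for baseline characteristics such as age and gender, if appropriate". No criterion for appropriateness is given, and the baseline ordinal category is not named.

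Part (a) of the same subsection fits an MMRM to change in the same scale and fixes "baseline Ordinal scale, age and gender as covariates".

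The related provisions are:
- **Randomisation.** SAP 3.2.1: "Subjects will be randomized 1:1 to receive either combination treatment with Gamunex-C plus SMT or SMT alone". Protocol 4.3.2 describes one central list, with the operator "selecting the next available randomization slot in the randomization list, starting at the top of the list". Neither document describes stratification.
- **Baseline spread.** Inclusion criterion 3(b) in Protocol 5.1 requires mechanical ventilation and/or supplemental oxygen, so the baseline category can be 2, 3 or 4.
- **Availability.** The scale is assessed at Screening/Baseline (Protocol 7.2.2). SAP 4.6 defines baseline as the last non-missing value before randomisation.
- **Fallback.** If proportional odds is rejected or the model fails to converge, the SAP adds a Wilcoxon rank-sum test, which is also unadjusted.

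**The concern.** The baseline category is the outcome scale measured before treatment. It is plausibly a strong predictor of status at Day 15 and Day 29, although the documents do not say how strong. If it is prognostic, a model with treatment alone loses power and its estimate moves with whatever imbalance the unstratified list produces.

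Optional wording also leaves open which odds ratio will be reported as the result. The trial is open-label and the SAP does not say when or by whom appropriateness will be judged, so the covariates could be settled after outcomes by arm are known. Prespecification closes that question whatever the gain in power.

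**Working it through.** **Plan's own figure.** There is none to reproduce. SAP 9 says "sample size estimation remains incompletely defined" and gives no effect size, power or outcome distribution.

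**Inputs from the documents.**
- About 100 subjects: "Approximately 100 subjects are allowed to be randomized as part of a humanitarian effort against COVID-19". With 1:1 allocation, that is about 50 per arm.
- Test level: "All statistical tests will be two-sided and tested at the 5% level of significance".
- Baseline categories 2, 3 and 4.

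**Inputs assumed.**
- Baseline mix of categories 2/3/4: 40/35/25%.
- Control outcome distribution at the middle baseline category, over outcome categories 1 to 7: 30/12/6/6/6/20/20%.
- Treatment odds ratio (OR): 1, 2 or 2.5.
- Prognostic OR per baseline category: 1 to 4.

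**1. Chance imbalance.** Let X and Y be independent binomials with n = 50 and share p starting in category 2. A gap of 10 points is |X − Y| ≥ 5, and a gap of 20 points is |X − Y| ≥ 10.

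| p | gap ≥ 10 points | gap ≥ 20 points |
|---|---|---|
| 30% | 32.6% | 3.8% |
| 40% | 35.8% | 5.2% |
| 50% | 36.8% | 5.7% |

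**2. Check on the simulation.** Whitehead's approximation for 1:1 allocation is power = Φ(ln OR × √V − 1.96), with V = (N/12)(1 − Σp̄³) and p̄ the mean of the two arms' category probabilities.
- OR 2: Σp̄³ = 0.0447, V = 8.333 × 0.9553 = 7.96, and 0.693 × √7.96 = 1.956. Power is Φ(−0.004) = 49.8%.
- OR 2.5: Σp̄³ = 0.0482, V = 7.93, and 0.916 × √7.93 = 2.581. Power is Φ(0.621) = 73.3%.

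Simulation with a non-prognostic baseline gives 52.1% and 72.5%, in reasonable agreement.

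**3. Power without and with baseline category.** Proportional-odds maximum likelihood with Wald tests, 1,500 trials per scenario; the Monte Carlo standard error of each power is about 1.3 points.

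| Prognostic OR per category | Treatment OR 2: without → with | Gain | Treatment OR 2.5: without → with | Gain |
|---|---|---|---|---|
| 1 | 52.1 → 50.9% | −1.2 | 72.5 → 72.0% | −0.5 |
| 1.5 | 50.1 → 50.9% | +0.8 | 71.9 → 72.5% | +0.6 |
| 2 | 44.5 → 48.4% | +3.9 | 65.1 → 70.7% | +5.6 |
| 3 | 39.1 → 46.5% | +7.4 | 60.3 → 70.0% | +9.7 |
| 4 | 33.7 → 45.7% | +12.0 | 54.3 → 67.1% | +12.8 |

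**4. Type I error over all trials.** It is 4.7 to 6.0% unadjusted and 4.3 to 6.1% adjusted. Both are about 5%, given a Monte Carlo error near 0.6 points.

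**5. Error given an imbalance.** In the most imbalanced fifth of trials (about 300 per scenario) with no treatment effect, at prognostic OR 2, 3 and 4, the unadjusted test rejects in 6.8, 8.2 and 13.5%. The adjusted test rejects in 3.2, 2.6 and 4.5%.

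With a true OR of 2, in the fifth whose baseline most favours control, the median unadjusted OR is 1.65, 1.50 and 1.35, and the adjusted OR is 2.01, 2.05 and 2.14. Part of that gap is non-collapsibility, because over all trials the median unadjusted OR is already 1.93, 1.83 and 1.76. The imbalance accounts for the drop from those values.

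**6. Age.** A second simulation assumed a baseline mix of 40/40/20%, a log-OR of 0.7 or 1.2 per category, and a log-OR of 0.6 per SD of age (700 trials per scenario, standard error about 1.9 points). At treatment OR 2, power went from 42% and 35% unadjusted, to 44% and 42% with category, to 51% and 47% with category and age. The last step comes from the assumed effect of age, not from baseline category.

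**The case against.** A reader might infer that the SAP leaves the baseline category out. It does not: age and gender are given as examples, so baseline category is permitted. The defect is that it is not prespecified.

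A reader might also infer that the unadjusted analysis is invalid. It is not. Averaged over randomisations its type I error is about 5%; what it loses is power, and accuracy in trials that happen to be imbalanced.

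Nor is baseline imbalance ignored for this scale. The MMRM in part (a) is baseline-adjusted and reports differences at Days 15 and 29. That is a partial answer only, because it treats the seven categories as equally spaced and does not yield the odds ratio. A change-from-baseline model also has its own reason to carry the baseline value, so the contrast between (a) and (b) does not prove an oversight.

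Other limits stand. The gain depends on a prognostic strength that the documents do not give, and it may be nil. Adjustment corrects for measured imbalance under the model; it does not remove imbalance. Nothing in the documents shows that covariates will be picked on results; they only leave room for it. The same optional wording appears in the SAP's ANOVA/ANCOVA analyses of ICU, hospital, ventilation and oxygen days. Finally, this is one secondary endpoint of a pilot with no power claim and no multiplicity control.

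**Conclusion.** The point holds as a gap in prespecification with a moderate consequence. Covariate adjustment in the Day 15/29 proportional-odds model is left to later judgement, although a baseline value of the same scale is collected, defined and already fixed in the companion model.

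The benefit of adding baseline category runs from about zero (prognostic OR per category of 1.5 or less) to about 4 to 13 points of power (2 to 4), for a true OR of 2 to 2.5 and 50 per arm. These figures rest on the assumed baseline mix and outcome distribution. When the category is not prognostic, any loss is within simulation error. A further gain from age requires age to be prognostic; gender was not simulated. The gap does not invalidate the planned test and does not touch the primary endpoint.

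**What to change.** Replace the optional sentence in SAP 6.2, Ordinal scales (b), with: *The model will include treatment, baseline Ordinal scale category, age and gender.* In the same place:
- State whether baseline category enters as a factor or a linear score, and how sparse categories are pooled.
- Note that the adjusted odds ratio is conditional on the covariates.
- Report the unadjusted odds ratio as a sensitivity result.
- Acknowledge that the Wilcoxon fallback remains unadjusted.

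The cost is a short SAP edit and no new data. There are two downsides. The main estimate becomes conditional rather than marginal, so the two odds ratios will differ even with perfect balance. The chance of non-convergence also rises slightly: with seven outcome categories the model has 6 intercepts plus treatment, age and gender (9 parameters), plus 1 or 2 for baseline category, giving 10 or 11 parameters for about 100 subjects.

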The proportional odds assumption will be tested using a score test at the two-sided alpha level of 0.05. In the event that the proportional odds assumption is not satisfied, given the anti-conservative nature of the score test, the proportional odds model will still be used for the analysis, and the results will be presented along with the score test p-value to help put these results in context. If the proportion odds assumption is rejected or if the proportional odds model fails to converge, a sensitivity or alternative analysis using a non-parametric Wilcoxon Rank Sum test will be performed to estimate the median difference between the treatment groups.

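### When proportional odds is rejected, the Wilcoxon fallback adds almost no independent evidence, and the median difference it is meant to estimate is undefined and coarse or unstable on a 7-point scale

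*SAP*

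**What the plan says.** Part (b) of the Ordinal scales text in SAP 6.2 has four steps.

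- Tabulation: "The proportion of subjects in each severity category of the 7-point Ordinal scale at Day 15 and Day 29 will be tabulated".
- Main comparison: "The difference in severity category distribution between treatment groups at Day 15 and Day 29 will be examined using proportional-odds cumulative logit model". Adjustment for age and gender is optional. "The estimated odds ratio and 95% CI will be presented".
- Assumption check: "The proportional odds assumption will be tested using a score test at the two-sided alpha level of 0.05". The SAP itself calls this score test anti-conservative, and so keeps the proportional-odds result after a rejection and shows it with the score-test p-value.
- Fallback, after either a rejection or non-convergence, is as follows: "a sensitivity or alternative analysis using a non-parametric Wilcoxon Rank Sum test will be performed to estimate the median difference between the treatment groups".

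The SAP does not say whether the median difference is the Hodges-Lehmann shift or the difference between the two sample medians, and it plans no interval for it. No effect estimate by cut-point is planned. Part (a) adds descriptive statistics and a repeated-measures model (MMRM) for mean change on the same scale. Protocol 9.1 names the Wilcoxon test only in general terms, for non-normally distributed variables.

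**The concern.** A sensitivity analysis prompted by failed proportional odds should show what the common odds ratio hides, namely how the effect differs between cut-points. The rank-sum test cannot do that, because it pools the cut-points in essentially the way the suspect model does. Agreement between the two could be taken as reassurance when it is close to automatic.

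The second problem is the estimate. A rank-sum test compares how often a subject in one arm has a better category than a subject in the other. It has no median difference attached to it, and on a scale with seven tied values either plausible estimator behaves poorly. A reported value of 0 could be read as no effect when the categories have in fact shifted.

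**Working it through.** **Inputs from the documents.** Two-sided 5% level (SAP 4: "All statistical tests will be two-sided and tested at the 5% level of significance"); about 100 subjects (SAP 9: "Approximately 100 subjects are allowed to be randomized as part of a humanitarian effort against COVID-19"); 1:1 allocation (SAP 3.2.1), hence about 50 per arm; seven categories. The plan gives no category probabilities, odds ratio or power for this endpoint, so there is no planned figure to reproduce.

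**Assumptions.** Control-arm probabilities for categories 1 to 7:

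- A: .25/.20/.08/.10/.07/.15/.15
- B: .30/.10/.04/.06/.05/.20/.25
- C: .20/.35/.12/.12/.08/.08/.05

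Each scenario was simulated 600 times at 50 per arm. Results are not conditioned on the proportional-odds check having rejected.

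**Step 1: the two tests nearly coincide.** With pooled category proportions p_j, take the rank sum W on the scale 2W/N.

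- Variance under the unadjusted proportional-odds score test: n1·n2·(1 − Σp_j³)/(3N).
- Tie-corrected Wilcoxon variance: n1·n2·(1 − Σp_j³)/(3(N − 1)).

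The numerators are the same, so score χ² = Wilcoxon χ² × N/(N − 1). At N = 100 the z-values differ by a factor √(100/99) = 1.0050. The gap in two-sided p-values is about 2·z·φ(z)·0.0050, largest near z = 1: 2 × 0.242 × 0.0050 = 0.0024. The simulations gave the same maximum, 0.0024. This step does not depend on the assumed distributions. Against the likelihood-ratio test of the proportional-odds model, decisions at 0.05 agreed in 98.2-100% of simulated trials, and in 99.2-99.3% when proportional odds was violated.

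**Step 2: the estimate, true common odds ratio 2.**

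| Distribution | Wilcoxon p<.05 | Hodges-Lehmann exactly 0 | Hodges-Lehmann 0 or ±1 | Sample-median difference 0 or ±1 | Range of sample-median difference |
|---|---|---|---|---|---|
| A | 49.3% | 27.2% | 92.7% | 22.5% | -2 to +4 |
| B | 45.2% | 51.2% | 97.8% | 37.8% | -1 to +5 |
| C | 49.7% | 33.7% | 98.3% | 48.5% | -1 to +3 |

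Over all scenarios run, Hodges-Lehmann was 0 or ±1 in 84-100% of trials. The difference of sample medians was 0 or ±1 in only 13-81%. The first is coarse; the second is unstable.

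**Step 3: non-proportional patterns.** Start from B, halve deaths from 30% to 15%, and place those subjects in category 2 (invasive ventilation or ECMO).

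- Odds ratio for death: (.15/.85)/(.30/.70) = 0.41.
- Every other cut-point: odds ratio 1, because death or ventilation stays at 30% + 10% = 15% + 25% = 40%.
- Mann-Whitney probability: the favourable excess is .25 × .30 − .15 × .10 = .06, so 0.5 + .06/2 = 0.53.
- Simulated: Wilcoxon rejected in 9.3% and proportional odds in 10.0%; Hodges-Lehmann was exactly 0 in 80.7%; the difference of sample medians ran from -4 to +4. Repeat runs, some with other assumed distributions, gave Wilcoxon 7-10% and Hodges-Lehmann zero in 73-83%.

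In a crossing pattern, deaths fall from 30% to 15% but subjects out of hospital also fall, from 45% to 30%. The odds ratio is 0.41 for death and (.70/.30)/(.55/.45) = 1.91 for hospitalised or dead. Wilcoxon rejected in 5.0% and proportional odds in 5.8%. Neither shows that the two ends of the scale moved in opposite directions.

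**The case against.** The strongest reply is that the fallback is a supplement and that the patterns above are visible elsewhere. Much of this stands.

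- A reader might infer that the ordinal endpoint is left with no usable analysis. The documents do not support that. The category table, the retained odds ratio with CI and the MMRM are all reported.
- A reader might infer that a mortality benefit would be lost. It would not. Day 29 death is the primary endpoint (SAP 6.1), with Fisher's exact test and an exact CI for the risk difference. For 30% versus 15% at 50 per arm, Fisher's power is 35% (an uncorrected chi-square gives 44%), whatever the ordinal fallback does. Hospital discharge has cumulative incidence with CIs at Days 15 and 29 and death as a competing event, which comes close to the hospitalised-or-dead cut-point. Death or invasive ventilation has no close equivalent.
- A reader might infer that the Wilcoxon p-value is invalid once proportional odds fails. It is not. It remains a valid test of equal distributions, and it is a genuine fallback for non-convergence.
- The near-identity is with the unadjusted model. With age and gender adjustment, which the SAP allows, the two tests can differ.
- Always 0 or 1 would be too strong. It fits Hodges-Lehmann only, and a significant Wilcoxon result seldom came with a shift of 0 (at most 2.6% of significant trials in scenarios with an effect).

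What these points leave untouched is that the tabulated proportions carry no between-group estimate or interval, that the MMRM also averages over cut-points, and that the stated purpose of the fallback is not something a rank-sum test achieves.

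**Conclusion.** The concern holds in a limited form. After a rejection of proportional odds, the Wilcoxon test is not an independent check on the unadjusted model: p-values lie within 0.0024 of its score test at 50 per arm, by algebra. The quantity it is said to estimate is unnamed, has no interval, and is either coarse (Hodges-Lehmann exactly 0 in 27-51% of trials at a true odds ratio of 2) or unstable (sample medians differing by -2 to +5). These percentages rest on assumed category distributions and should be read as ranges. The impact is modest: a conditional analysis of one secondary endpoint in a pilot of about 100 subjects with no multiplicity adjustment, and no primary conclusion depends on it. It is still worth changing, because the method does not do its stated job and a better one needs no new data.

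**What to change.** In SAP 6.2, Ordinal scales (b):

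1. At Days 15 and 29, whether or not the score test rejects, report cumulative odds ratios or risk differences with 95% CIs at stated cut-points beside the common odds ratio. Include at least death, death or invasive ventilation/ECMO, and hospitalised or dead. Label them descriptive.
2. Keep the Wilcoxon p-value as the fallback for non-convergence.
3. Replace the median difference with the Mann-Whitney probability that a subject in the IVIG arm has the better category, ties counted half, with a 95% CI. State that it is a summary measure and not a check on proportional odds. The value of 0.53 in the deaths-to-ventilated example shows that it averages over cut-points too.

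The cost is SAP wording and one table. The drawback is imprecision at sparse cut-points. With the assumed 15 versus 7.5 expected deaths of 50, the log odds ratio has standard error √(1/15 + 1/35 + 1/7.5 + 1/42.5) = 0.50, so an odds ratio of 0.41 would carry a 95% CI of about 0.15 to 1.10.

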### **Number of subjects developed ARDS**

Berlin criteria for ARDS will be assessed on Days 1, 5, 15, and 29. The presence of ARDS and the degree of ARDS by Berlin criteria (Mild, Moderate, Severe) will be tabulated by treatment group at each visit.

